2.4.4.3 Multiplicity issues

No adjustments for multiplicity are planned for this Phase 2a study. More specifically, no adjustments will be made in comparing the multiple treatment groups based on the primary and secondary efficacy endpoints and no adjustments will be made for the subgroup analyses.

2.4.4.4 Additional efficacy analysis(es)

2.4.4.4.1. Change from baseline analysis in other continuous endpoints

Change from baseline in AM/PM PEF, FVC, FEF 25%-75%, ACQ-5 score, AQLQ(S) domain scores, AQLQ(S) overall score, RQLQ(S) domain scores, RQLQ(S) overall score, AM/PM asthma symptom score, number of nocturnal awakenings, and number of inhalations/day of albuterol or levalbuterol for symptom relief will be analyzed using the MMRM approach described above. Inclusion of data will follow the rules listed in [Table 5](#). The covariates will be treatment, baseline eosinophil strata, region, background ICS dose level at randomization, visit, treatment-by-visit interaction, baseline value and baseline-by-visit interaction. Gender and height will also be included in the model for spirometry endpoints. No imputation will be performed on missing values.

Descriptive statistics including number of patients, mean, standard error, and LS means will be provided for each treatment group. Difference in LS means and the corresponding 95% CI and p-value will be provided for each pairwise treatment comparison.

A responder analysis will also be performed for ACQ-5 and AQLQ(S) endpoints, where responder status is determined based only on data included according to the rules in [Table 5](#). A logistic regression model will be used to compare the percentage of patients reaching the MCID (responders) at Weeks 4, 8, and 12 for ACQ-5 and AQLQ(S) overall scores. For ACQ-5, a patient is considered as a responder if change from baseline in ACQ-5 is ≤ -0.5 , or as a non-responder if change from baseline is > 0.5 or missing. For AQLQ(S), a patient is considered as a responder if change from baseline in AQLQ(S) global score is ≥ 0.5 , or as a non-responder if change from baseline is < 0.5 or missing.

At each time point, the model will include treatment, baseline score, baseline eosinophil strata, region and background ICS dose level at randomization. Odds ratio, the corresponding 95% CI and p-value will be derived for each pairwise treatment comparison. Descriptive statistics including number and percentage of responders will also be provided.

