2.1.3.2.5 Patient-reported outcomes

The questionnaires listed below will be administered at on-site visits. Responses will be recorded in the electronic diary. Based on the device design, no partial missing data is expected.

ACQ-5

The ACQ was designed to measure both the adequacy of asthma control and change in asthma control which occurs either spontaneously or as a result of treatment.

The ACQ-5 has 5 questions: 1. Frequency in past week awoken by asthma during the night, 2. Severity of asthma symptoms in the morning, 3. Limitation of daily activities due to asthma, 4. Shortness of breath due to asthma and 5. Wheeze. Patients are asked to recall how their asthma has been during the previous week and to respond to the symptom questions on a 7-point scale (0=no impairment, 6=maximum impairment) (see [Appendix C](#)).

A global score is calculated: the questions are equally weighted and the ACQ-5 score is the mean of the 5 questions and, therefore, between 0 (totally controlled) and 6 (severely uncontrolled).

Higher score indicates lower asthma control. Patients with a score below 1.0 reflect adequately controlled asthma and patients with scores above 1.0 reflect inadequately controlled asthma. On the 7-point scale of the ACQ-5, a change or difference in score of 0.5 at patient level is the smallest change that can be considered clinically important, corresponding to the Minimal Clinically Important Difference (MCID) defined by the developer.

AQLQ(S)

The AQLQ(S) was designed as a self-administered patient reported outcome to measure the functional impairments that are most troublesome as a result of their asthma.

The instrument is comprised of 32 items (see [Appendix D](#)), each rated on a 7-point Likert scales from 1 to 7. Patients are asked to recall how their asthma has been during the previous 2 weeks. The AQLQ(S) has 4 domains. The domains and the number of items in each domain are as follows:

- Symptoms (12 items)
- Activity limitation (11 items)
- Emotional function (5 items)
- Environmental stimuli (4 items)

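### The ACQ-5 non-responder cut-off has lost its minus sign, so patients with no clinically important change are neither responders nor non-responders

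*SAP*

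**What the plan says.** SAP Section 2.4.4.4.1 adds a responder analysis for ACQ-5 and AQLQ(S): "A logistic regression model will be used to compare the percentage of patients reaching the MCID (responders) at Weeks 4, 8, and 12". It defines the two outcomes as follows.

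- **ACQ-5, responder:** "a patient is considered as a responder if change from baseline in ACQ-5 is ≤ -0.5".
- **ACQ-5, non-responder:** "or as a non-responder if change from baseline is > 0.5 or missing".
- **AQLQ(S), responder:** "a patient is considered as a responder if change from baseline in AQLQ(S) global score is ≥ 0.5".
- **AQLQ(S), non-responder:** "or as a non-responder if change from baseline is < 0.5 or missing".

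SAP Section 2.1.3.2.5 fixes the direction and scale of the ACQ-5: "Higher score indicates lower asthma control"; "the questions are equally weighted and the ACQ-5 score is the mean of the 5 questions"; and "a change or difference in score of 0.5 at patient level is the smallest change that can be considered clinically important". Each item is scored 0 to 6.

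**The concern.** Improvement on the ACQ-5 is a negative change, so the responder cut-off of -0.5 has the right sign. Its complement is any change above -0.5. The printed non-responder cut-off is +0.5, which is clinically important worsening. The band between the two holds patients who were measured and did not improve by the MCID, and the rule gives them no outcome.

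The rule is also inconsistent within itself. A patient with no Week 12 score counts as a non-responder, while a patient measured as unchanged counts as nothing.

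If the sentence is programmed literally and unclassified records fall out, the denominator loses observed non-responders. Percentages then rise in every arm that has such patients. The odds ratio, confidence interval and p-value for each of the five comparisons in SAP Table 4 come from a subset selected on the post-randomisation outcome itself.

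**Working it through.** The documents give no ACQ-5 responder rate, so there is no plan figure to reproduce. The check has two parts: whether the rule covers every possible change, and how large the effect could be.

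**1. Coverage.** The score is the mean of five integer items from 0 to 6, so a change is a multiple of 1/5 = 0.2 between -6 and +6. Each possible value was tested against the rules.

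| Change in ACQ-5 | Rule as printed | Non-responder set to > -0.5 |
|---|---|---|
| -0.6 or lower | responder | responder |
| -0.4, -0.2, 0.0, +0.2, +0.4 | **no class** | non-responder |
| +0.6 or higher | non-responder | non-responder |
| missing | non-responder | non-responder |

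With the sign restored, no value is left over. The AQLQ(S) pair (≥ 0.5 against < 0.5 or missing) leaves none over as printed. No other section of the protocol or SAP assigns the five values in the gap.

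**2. Size, by illustration.** The means, SD and missing-data rates below are assumptions. None is an ACQ-5 figure from the documents. Changes are taken as normal with mean -0.9 (active) and -0.5 (placebo) and SD 0.9. Unclassified patients are dropped.

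Active arm:
- P(change ≤ -0.5) = Φ((-0.5 + 0.9)/0.9) = Φ(0.444) = 0.672
- P(change > 0.5) = 1 - Φ((0.5 + 0.9)/0.9) = 1 - Φ(1.556) = 0.060
- unclassified = 1 - 0.672 - 0.060 = 0.268, or 27%

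Placebo arm:
- P(change ≤ -0.5) = Φ(0) = 0.500
- P(change > 0.5) = 1 - Φ(1.111) = 0.133
- unclassified = 1 - 0.500 - 0.133 = 0.367, or 37%

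Correct rule: 67% v 50%; odds ratio (0.672/0.328)/(0.500/0.500) = 2.05.

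Printed rule: 0.672/(0.672 + 0.060) = 92% and 0.500/(0.500 + 0.133) = 79%; odds ratio 2.99 before rounding of the inputs.

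With a fraction m missing and counted as non-response, responders are (1 - m)·P(≤ -0.5) and non-responders under the printed rule are (1 - m)·P(> 0.5) + m:

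| Missing, active / placebo | Correct rule | Odds ratio | Printed rule | Odds ratio |
|---|---|---|---|---|
| 0% / 0% | 67% v 50% | 2.05 | 92% v 79% | 2.99 |
| 20% / 20% | 54% v 40% | 1.74 | 68% v 57% | 1.66 |
| 14% / 40% | 58% v 30% | 3.19 | 75% v 38% | 4.83 |

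The 14% and 40% in the last row borrow the LOAC rates assumed for sample size in SAP Section 1.3, as if every LOAC patient had no usable score.

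**3. Sensitivity to the SD.** With the same means and nothing missing, SDs from 0.8 to 1.2 leave 25% to 39% of patients per arm unclassified. The odds ratio is 2.24 down to 1.71 under the correct rule and 3.65 down to 2.10 under the printed one. With 20% missing in both arms it goes from 1.86 to 1.70 at SD 0.8, and stays at 1.53 at SD 1.2. Responder rates rose in every scenario tried.

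**The case against.** The strongest reply is that the results go wrong only if a programmer codes the sentence literally and then discards patients with valid scores. Several parts of the SAP point the other way. The responder cut-off is right, and the stated aim is the percentage of patients who reach the MCID. Missing scores count as non-response, which implies a full denominator. SAP Section 2.4.4 says every efficacy endpoint uses the mITT population. The default in SAP Section 2.5.3 of leaving patients out of percentages concerns missing data, and these patients have data. Code that sets 1 for a change of -0.5 or lower and 0 otherwise gives the right answer. The AQLQ(S) rule that exposes the slip also tells a careful reader what was meant.

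The analysis is also minor. The listed ACQ-5 endpoint is change from baseline, and the protocol defines responder proportions for AQLQ(S) and RQLQ(S) but not for ACQ-5. P-values are nominal in a Phase 2a study. The illustration uses assumed values, and the unequal-missingness row does not suit Week 4, when background withdrawal only begins. SAP Table 5 also keeps the end-of-treatment value for LOAC without rescue medication. Finally, a minus sign could have been lost when the PDF was read.

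Most of this stands as a limit on the consequence. It does not remove the gap. The SAP is the programming specification, and a correct result should not depend on departing from it without record. The extraction explanation is unlikely, because the minus in the responder cut-off of the same sentence survived; the source file would settle it.

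**Conclusion.** The concern holds. The ACQ-5 non-responder definition is not the complement of the responder definition, and five attainable changes around zero have no class. That follows from the text, the scale direction and the scoring grid, without any assumption.

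The numerical effect is conditional on literal programming with unclassified patients dropped. Under that condition, and under the assumed distributions, about a quarter to two fifths of each arm is lost when nothing is missing, and responder rates are overstated in every scenario tried. The odds ratio is distorted by an amount and in a direction that depend on missingness: 2.05 to 2.99 with none, 1.74 to 1.66 with 20% in each arm, and 3.19 to 4.83 with 14% and 40%.

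The scope is the ACQ-5 responder analysis at Weeks 4, 8 and 12. The primary LOAC analysis, the FEV1 analyses, the ACQ-5 repeated-measures model, the AQLQ(S) responder analysis and the sample size do not depend on it. The correction should be made because the error is certain and costs almost nothing to remove, not because it threatens the primary conclusion.

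**What to change.** In SAP Section 2.4.4.4.1, define an ACQ-5 non-responder as a patient whose change from baseline is > -0.5 or missing. Then check that the derivation code gives every mITT patient exactly one outcome at each of Weeks 4, 8 and 12, so that responders plus non-responders equal the arm total. If the analysis has already been run, establish what was coded, rerun it if the printed rule was used, and record the correction.

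The cost is one character in the SAP and a short check of the program. Design, data collection and sample size are unchanged.

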2.4.4.4.2. CompEx

Time to CompEx will be analyzed in an exploratory fashion using the same Cox model described in [Section 2.4.4.1](#).

2.4.5 Analyses of safety data

The summary of safety results will be presented by treatment group.

General common rules

All safety analyses will be performed on the safety population as defined in [Section 2.3.2](#), unless otherwise specified, using the following common rules:

- Safety data in patients who do not belong to the safety population will be listed separately
- The baseline value is defined as the last available value prior to the first dose of the IMP
- The potentially clinically significant abnormality (PCSA) values are defined as abnormal values considered medically important by the Sponsor according to predefined criteria/thresholds based on literature review and defined by the Sponsor for clinical laboratory tests, vital signs, and ECG (PCSA version dated May 2014, see [Appendix A](#))
- PCSA criteria will determine which patients had at least 1 PCSA during the treatment-emergent adverse event period, taking into account all evaluations performed during the treatment-emergent adverse event period, including nonscheduled or repeated evaluations. The number of all such patients will be the numerator for the on-treatment PCSA percentage
- The treatment-emergent PCSA denominator by group for a given parameter will be based on the number of patients assessed for that given parameter in the TEAE period by treatment group on the safety population.
- For quantitative safety parameters based on central laboratory/reading measurements, descriptive statistics will be used to summarize results and change from baseline values by visit and treatment group. Summaries will include the endpoint value. The endpoint value is defined as the value collected at or just prior to the last dose date + 14 days, or at end of treatment visit, whichever comes later. If this value is missing, this endpoint value will be the closest value prior to the last dose intake. The worst value is defined as the nadir and/or the peak post-baseline (up to last administration of IMP) according to the direction (minimum or maximum) of the abnormality as defined in the PCSA list
- The analysis of the safety variables will be essentially descriptive and no systematic testing is planned.

All safety values including unscheduled measurements will be assigned to the appropriate safety analysis visit window defined in [Section 2.5.4](#).

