#### **11.4.3.1.3 Clinical laboratory evaluation, vital signs, and electrocardiogram data**

Results and change from baseline for the parameters will be summarized by treatment group for baseline and each post baseline time point, endpoint, minimum, and maximum value. Summary statistics will include number of patients, mean, SD, median, Q1, Q3, minimum, and maximum.

The proportion of patients who had at least 1 incidence of PCSA at any time during the treatment emergent period will be summarized by treatment group. Shift tables showing changes with respect to the baseline status will be provided.

Listings will be provided with flags indicating clinically out-of range values, as well as PCSA values.

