2.1.4 Safety endpoints

The safety analysis will be based on the reported adverse events (AEs) and other safety information, such as clinical laboratory data, vital signs, electrocardiogram (ECG), etc.

Observation period

The observation period will be divided into 4 epochs:

- The **screening** epoch is defined as the time from the signed informed consent date up to the first administration of the IMP.
- The **treatment** epoch is defined as the time from the first administration of the IMP to the last administration of the IMP + 14 days.
- The **residual treatment** epoch is defined as the time from the last administration of the IMP + 15 days to the last administration of the IMP + 154 days.

The treatment-emergent adverse event (TEAE) period will include both **treatment** and **residual treatment** epochs.

- The **post-treatment** epoch is defined as the period of time starting the day after the end of the treatment-emergent adverse event period up to the patient's end of study (defined as last protocol-planned visit or the resolution/stabilization of all serious adverse events and adverse events with pre-specified monitoring).

The on-study observation period is defined as the time from start of treatment until the end of the study.

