2.4.5.3 Analyses of laboratory variables

The summary statistics (including number, mean, median, Q1, Q3, SD, minimum and maximum) of all laboratory variables (central laboratory values and changes from baseline) will be calculated for each visit or study assessment (baseline, each post-baseline time point, and last on-treatment) by treatment group. For each continuous parameter listed in [Section 2.1.4.3](#), mean changes from baseline with the corresponding standard error will be plotted over time in each treatment group. This section will be organized by biological function as specified in [Section 2.1.4.3](#).

The incidence of PCSAs (list provided in [Appendix A](#)) at any time during the TEAE period will be summarized by biological function and treatment group whatever the baseline level and/or according to the following baseline status categories:

- Normal/missing
- Abnormal according to PCSA criterion or criteria

For parameters for which no PCSA criteria are defined, similar table(s) using the normal range will be provided.

Laboratory measurements obtained at either scheduled or unscheduled visits will be used in analyses of PCSA. In addition, both centralized and local test results will be used. Centralized data will be used preferentially to the local measures in the analysis when several measurements are performed on the same date and at the same time for a given laboratory test.

Listings will be provided with flags indicating the out of range values as well as the PCSA values.

Potential drug-induced liver injury

If there is any imbalance in the incidence of liver-related adverse events across the treatment groups, the following analysis of liver-related adverse events will be performed.

The liver function tests, namely AST, ALT, alkaline phosphatase, and total bilirubin will be used to assess possible drug-induced liver toxicity. The proportion of patients with PCSA values at any post-baseline visit will also be displayed by duration of exposure for each treatment group.

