2.5.5 Unscheduled visits

Unscheduled visit measurements of laboratory data, vital signs, and ECG will be included in the by-visit summaries, computation of baseline, worst values, and PCSAs.

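### SAP 2.4.5 ends the worst-value window at the last dose, so a completer's Week 12/EOT lab and ECG values are left out of the worst value and the endpoint value can be more extreme than it

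*SAP*

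**What the plan says.** The general rules in SAP 2.4.5 contain one bullet whose scope is stated as "For quantitative safety parameters based on central laboratory/reading measurements". That covers central laboratory results and also ECGs, which SAP 2.1.4.5 says are read centrally. The bullet defines two derived values.

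- **Endpoint value:** the "value collected at or just prior to the last dose date + 14 days, or at end of treatment visit, whichever comes later". If it is missing, the closest value before the last dose is used.
- **Worst value:** "The worst value is defined as the nadir and/or the peak post-baseline (up to last administration of IMP").

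SAP 2.1.4 defines the treatment epoch on the longer basis: the "epoch is defined as the time from the first administration of the IMP to the last administration of the IMP + 14 days". PCSA incidence in SAP 2.4.5 uses the whole TEAE period, which runs to 154 days after the last dose.

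Two places bear on whether the worst value is used. Protocol 11.4.3.1.3 asks for summaries at "baseline and each post baseline time point, endpoint, minimum, and maximum value". SAP 2.5.5 says that unscheduled measurements enter the "computation of baseline, worst values, and PCSAs".

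**The concern.** Two values defined in one bullet stop at different times, and no reason is given. The later stop belongs to the endpoint value. A patient's endpoint can therefore be higher than the peak or lower than the nadir reported for the same parameter, which contradicts what a worst value means.

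The gap is not an occasional accident of timing. No central laboratory sample or ECG is scheduled between the last dose and Visit 14, so the shorter window drops the last on-treatment assessment for everyone who completes. At stake is whether a minimum, maximum or worst-value summary of labs and ECG describes the full treatment period.

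**Working it through.** **Dosing days.** The visit-by-visit text in protocol 10.1.2 lists IMP administration at Visits 2, 4, 6, 8, 10 and 12, that is Days 1, 15, 29, 43, 57 and 71. Visits 13 and 14 have no dosing or kit step. The sampling text for Visit 14 does mention sampling before IMP, but the same words appear at Visits 15 and 17, where no dose is planned.

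**Check against the plan's own figures.**

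- Exposure (SAP 2.4.3.1: last dose − first dose + 14) = 71 − 1 + 14 = 84 days. Protocol 6.2.1 states 84 days.
- End of the treatment epoch = 71 + 14 = Day 85, which is Visit 14/EOT.
- End of the TEAE period = 71 + 154 = Day 225, which is Visit 17/EOS.

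Day 71 as the nominal last dose is consistent with all three.

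**Gap from last dose to Visit 14.** Visits in the treatment period have a window of ±3 days.

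- Nominal: 85 − 71 = 14 days
- Shortest: (85 − 3) − (71 + 3) = 82 − 74 = 8 days
- Longest: (85 + 3) − (71 − 3) = 88 − 68 = 20 days

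The gap is always positive, so Visit 14 is never inside the worst-value window for a completer. At its longest it also exceeds 14 days.

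**Scheduled on-treatment values, completer** (visit lists from SAP 2.1.4.3, 2.1.4.5 and 2.1.7):

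| Parameter | Scheduled post-baseline days to EOT | Inside worst-value window | Left out |
|---|---|---|---|
| Chemistry, most haematology | 29, 57, 85 | 29, 57 | 85 (1 of 3) |
| ECG | 29, 85 | 29 | 85 (1 of 2) |
| Eosinophils, neutrophils | 15, 29, 43, 57, 85 | 15, 29, 43, 57 | 85 (1 of 5) |

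For ECG, the scheduled part of the worst value is simply the Day 29 reading.

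**Early discontinuation.** Patients who stop for LOAC or another reason have their EOT assessments after the last dose, so samples taken then are outside the worst-value window as well. A patient last dosed on Day 1 or Day 15 has no scheduled post-baseline chemistry or ECG by that dose. Such a patient has no scheduled worst value for those parameters, yet has an endpoint value if the EOT visit takes place.

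**Which outputs could carry the rule.** The row list in SAP 2.4.5.3 is "baseline, each post-baseline time point, and last on-treatment", and 2.4.5.4 and 2.4.5.5 use the same list. None of them names a worst-value row. The remaining routes are the minimum and maximum in protocol 11.4.3.1.3 and the worst values in SAP 2.5.5.

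**The case against.** The strongest reply is that the definition hardly matters. The SAP's laboratory and ECG sections list no worst-value row, and the bullet itself names only the other quantity: "Summaries will include the endpoint value". The main abnormality analysis, PCSA incidence, uses the whole TEAE period. By-visit tables include Week 12, and listings flag abnormal values. On this view the sentence is close to unused and needs no more than an editorial note.

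Most of that stands, and it sets the grade. It does not remove the point. The protocol asks for endpoint, minimum and maximum together, and SAP 2.5.5 expects worst values to be computed. A programmer who follows 2.4.5 literally could produce a maximum lower than the endpoint shown beside it.

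A reader might infer more than the documents support, in three ways.

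- **That Week 12 safety data are lost.** They are left out of the worst value only.
- **That the peak eosinophil table and the ALT-versus-bilirubin graph in SAP 2.4.5.3 are cut at the last dose.** Neither states a cut, and the same section uses post-baseline elsewhere without one. The text does not show that they lose Week 12.
- **That the share of patients whose endpoint exceeds their worst value can be stated.** The documents give no variability for these parameters. Any figure would need assumptions of no time trend and no tied values. The first is doubtful for eosinophils, because ICS is tapered to zero over Weeks 6 to 9.

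**Conclusion.** The rule is wrong as written, and the matter is minor. For every completer, the Week 12/EOT value is excluded from the worst value of each central laboratory and ECG parameter, at the fractions shown in the table. This rests only on the visit schedule, the ±3-day windows and the wording of one bullet; it needs no model. The counts cover scheduled values. An unscheduled value taken by the last dose would count towards the worst value, and one taken after it would not.

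The consequence is limited to descriptive worst-value or minimum/maximum summaries. No efficacy analysis or formal safety test depends on it.

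**What to change.** In SAP 2.4.5, replace the parenthesis that ends the worst value at the last IMP administration with the endpoint-value window: last dose date + 14 days or the EOT visit, whichever is later. The endpoint value then always lies inside the period searched for the worst value. The EOT clause is needed because Visit 14 can fall up to 20 days after the last dose, which 14 days alone would miss. A completer's worst value would then use Days 29, 57 and 85 for chemistry, and Days 29 and 85 for ECG.

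Using the TEAE period, as for PCSA, would also remove the contradiction. It would add the follow-up values, namely labs at Days 141 and 225 and the ECG at Day 225. If the shorter window was intended, the SAP should say why.

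Optionally, a sentence in SAP 2.4.5.3 could give the window for the eosinophil and ALT/bilirubin peaks. That would be a clarification, not a correction.

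The cost is one phrase in the SAP, with no new data.
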